#### Outcomes and Analysis:

We will collect data on implementation such as completeness of the peer delivery, satisfaction of the patients, patient activation, and fidelity of delivery strategy. Patient satisfaction will be measured through a survey adapted from the AIDS Clinical Research Trials Group tool used extensively throughout Kenya and in the Harambee study. Patient activation will be measured through the Patient Activation Measure assessment developed by Insignia Health. Fidelity will be measured as quantity and quality of intervention delivery as intended, comprised of three components: confirmed medication delivery documented by patient e-signature, peer completion of the HIT form, and quality of data entry into the HIT form, which will be assessed by checking for completeness, accuracy and coherent filling of the responses. Completeness of delivery will include these metrics of fidelity in addition to other quality assurance measures centering on medication packaging as well which will be done by the research assistant as the study goes on. We will also conduct surveys with patients, clinicians, and peer delivery agents, focusing on contextual issues impacting implementation, suggestions for modifications, and concepts of feasibility, that is, if the process of delivery and counseling has been successful or not successful in all the settings and the perceived ease of implementing the intervention. We will also evaluate the impact of the pilot on absolute mean change in SBP and medication adherence. The primary adherence outcome is the pill count adherence ratio, which is the proportion of prescribed doses taken over a 1-month time period, assessed at the end of the pilot.

#### **Design Team Meeting #6: Iteration II**

##### Session A:

- DT members will engage in icebreaker activities and review previous discussions
- PT4A research team will present and discuss findings from pilot study
- DT will group issues raised in FGDs and from study investigators into themes and propose intervention updates

Session B:

- DT will create a final intervention model and submit this to the study investigators, research team, and Informatics team
- The research team will conduct individual surveys with DT members to evaluate their experience during the HCD process

The research team and Informatics team will be responsible for creating the final intervention model that will be used for more widespread implementation.

## APPENDIX B. STUDY INTERVIEW QUESTIONNAIRES

### Peers and Technology for Adherence, Access, Accountability, and Analytics (PT4A) Study

#### Study Instrument: Acceptability of Intervention Measure (AIM) for Patients Living with Hypertension

Study ID:	Date:		
Age:	Gender:		
1. Education/ Elimu			
 Primary/ Shule ya Msingi	 No formal education/ Hakuna elimu rasmi		
 Beyond secondary/ Zaidi ya Shule ya Upili	 Secondary/ Shule ya Upili		
maalum	 Special training e.g Trade. Insert Mafunzo kwa mfano biashara		
2. What is your main source of income?/ Chanzo chako kikuu cha mapato ni nini?			
 Farming/ Ukulima	 Business/Trade/Biashara	 Teacher/	
Uwaalimu			
 Health worker/ Mfanyakazi wa afya	 Other/s (Insert): Ingine		
3. What is your estimated monthly income in KES?/ Je! Mapato yako ya kila mwezi yanakadiriwa ngapi			
 KES? <1,000	 1,000-2,999	 3,000-4,999	 5,000-9,999
 >10,000			
4. How long have you been living with hypertension/pressure in months? Umeishi kwa muda gani na shinikizo la damu / shinikizo (kwa miezi)			
 <6 months/ Miezi sita	 Between 6 months – 1year/ Kati ya miezi sita na mwaka		
 Between 1-2 years/ Kati ya mwaka mmoja na mbili?  >2 years/ Zaidi ya miaka mbili?			
5. Where do you mainly seek treatment for hypertension/pressure?/ Unapata wapi matibabu ya shinikizo la damu			
 Health facility/ Kituo cha afya	 Pharmacy (over the counter medication) Duka la dawa		
 Herbalist / Mtaalam wa mimea	(juu ya dawa ya kaunta)		
 Not yet sought care/ Bado sijatafuta huduma	 Other specify/ Nyingine taja		
6. About how long would it take to get from your home to the nearest chemist/pharmacy if you walked to them? Je! Itachukua muda gani kutoka nyumbani kwako kwenda kwa duka la dawa lilokaribu ukitembea?			
 Less than 15 minutes/ Chini ya dakika 15	 16-30 minutes/ Dakika 16-30		
 31 minutes to an hour/ dakika 31 hadi saa moja	 More than one hour/ Zaidi ya saa moja		
7. About how long would it take to get from your home to the nearest healthcare facility if you walked to them?/ Je! Itachukua muda gani kutoka nyumbani kwako kwenda kituo cha huduma ya afya kilicho karibu ikiwa utatembea kuelekea huko?			
 Less than 15 minutes/ Chini ya dakika 15	 16-30 minutes/ Dakika 16-30		

31 minutes to an hour/ dakika 31 hadi saa moja

More than one hour/ Zaidi ya saa moja

**Instructions to Study Personnel:** *Read all questions aloud to the patient and record answers on questionnaire form.*

You were selected to take part in this survey because we value the knowledge you have on our topic of discussion. I kindly request for your honest opinions and ideas. There is no wrong or right response. You should feel free to say whatever you think and feel.

*There is a plan to start a project that will support people living with hypertension/pressure at the community level. The purpose of the project is to assist these individuals take hypertension/pressure medication their as required through a peer-led project. A peer will be someone who is living with hypertension/pressure in the community and has been successful in managing their hypertension. The peer will be responsible for a number of things:*

- *Deliver hypertension medication to people living with hypertension/pressure at their most convenient location (door-to-door medication delivery).*
- *Provide psychological support to people living with hypertension/pressure during medication delivery and whenever needed.*
- *Record the health progress of people living with hypertension/pressure in a mobile device whenever they are in contact with a person living with hypertension/pressure.*
- *Using the mobile device, communicate with a clinician where the individuals living with hypertension receive care to discuss their health progress.*
- *Whenever necessary enable a conversation (either audio or video) between the clinician and the patient using the mobile device at the patient's convenient location.*
- *Insert the revised prototype*

	Completely disagree	Disagree	Neither agree nor disagree	Agree	Completely agree
1. The HIT-Peer Delivery system meets my needs	①	②	③	④	⑤
2. The HIT-Peer Delivery system is appealing to me.	①	②	③	④	⑤
3. I like the HIT-Peer Delivery system.	①	②	③	④	⑤
4. I would like to be enrolled in the HIT-Peer Delivery system.	①	②	③	④	⑤

**With this revisions to our PT4A strategy, will this prototype do the following for you.**

### Intervention Appropriateness Measure (IAM)

	Completely disagree	Dis- agree	Neither agree nor dis- agree	Agree	Com- pletely agree
The HIT-Peer Delivery system seems fitting.	①	②	③	④	⑤
The HIT-Peer Delivery system seems suitable.	①	②	③	④	⑤
The HIT-Peer Delivery system seems applicable.	①	②	③	④	⑤
The HIT-Peer Delivery system seems like a good match.	①	②	③	④	⑤
Total Score:					

**Peers and Technology for Adherence, Access, Accountability, and Analytics (PT4A)  
Study**

**Study Instrument: Acceptability of Intervention Measure (AIM) for Health Care Team**

Study ID:	Date:				
Age:	Gender:				
1. What is your primary role at the facility?   MO  CO  Nurse  Other staff (specify) _____					
2. How long have you served as a health provider for Hypertensive patients?					
3. What is your interaction with patients living with Hypertension?					
Instructions to Study Personnel: Read all questions aloud to the healthcare provider and record answers on questionnaire form.					

You were selected to take part in this survey because we value the knowledge you have on our topic of discussion. I kindly request for your honest opinions and ideas. There is no wrong or right response. You should feel free to say whatever you think and feel.
 
There is a plan to start a project that will support people living with hypertension/pressure at the community level. The purpose of the project is to assist these individuals take hypertension/pressure medication their as required through a peer-led project. A peer will be someone who is living with hypertension/pressure in the community and has been successful in managing their hypertension. The peer will be responsible for a number of things:
 

• Deliver hypertension medication to people living with hypertension/pressure at their most convenient location (door-to-door medication delivery).

• Provide psychological support to people living with hypertension/pressure during medication delivery and whenever needed.

• Record the health progress of people living with hypertension/pressure in a mobile device whenever they are in contact with a person living with hypertension/pressure.

• Using the mobile device, communicate with a clinician where the individuals living with hypertension receive care to discuss their health progress.

• Whenever necessary enable a conversation (either audio or video) between the clinician and the patient using the mobile device at the patient's convenient location.

• Insert the revised prototype

					
	Completely disagree	Disagree	Neither agree nor disagree	Agree	Can't say

1. The HIT-Peer Delivery system meets the patients needs	①	②	③	④	
2. The HIT-Peer Delivery system is appealing to both the patient and I healthcare provider	①	②	③	④	
3. I like the HIT-Peer Delivery system.	①	②	③	④	
4. I would like my patients enrolled in the HIT-Peer Delivery system.	①	②	③	④	

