 31 minutes to an hour/ dakika 31 hadi saa moja	 More than one hour/ Zaidi ya saa moja			
8. About how long would it take to get from your home to the nearest healthcare facility if you walked to them?/ Je! Itachukua muda gani kutoka nyumbani kwako kwenda kituo cha huduma ya afya kilicho karibu ikiwa utatembea kuelekea huko?				
 Less than 15 minutes/ Chini ya dakika 15	 16-30 minutes/ Dakika 16-30			
 31 minutes to an hour/ dakika 31 hadi saa moja	 More than one hour/ Zaidi ya saa moja			

**Instructions to Study Personnel:** *Read all questions aloud to the patient and record answers on questionnaire form.*

You were selected to take part in this survey because we value the knowledge you have on our topic of discussion. I kindly request for your honest opinions and ideas. There is no wrong or right response.

You should feel free to say whatever you think and feel.

*There is a plan to start a project that will support people living with hypertension/pressure at the community level. The purpose of the project is to assist these individuals take hypertension/pressure medication their as required through a peer-led project. A peer will be someone who is living with hypertension/pressure in the community and has been successful in managing their hypertension. The peer will be responsible for a number of things:*

- *Deliver hypertension medication to people living with hypertension/pressure at their most convenient location (door-to-door medication delivery).*
- *Provide psychological support to people living with hypertension/pressure during medication delivery and whenever needed.*
- *Record the health progress of people living with hypertension/pressure in a mobile device whenever they are in contact with a person living with hypertension/pressure.*
- *Using the mobile device, communicate with a clinician where the individuals living with hypertension receive care to discuss their health progress.*
- *Whenever necessary enable a conversation (either audio or video) between the clinician and the patient using the mobile device at the patient's convenient location.*
- *Insert the revised prototype*

	Completely disagree	Disagree	Neither agree nor disagree	Agree	Complete agree
1. The HIT-Peer Delivery system meets my needs	①	②	③	④	⑤
2. The HIT-Peer Delivery system is appealing to me.	①	②	③	④	⑤

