3. I like the HIT-Peer Delivery system.	①	②	③	④	⑤
4. I would like to be enrolled in the HIT-Peer Delivery system.	①	②	③	④	⑤

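### As printed, the staff acceptability form (AIM) has no option for full agreement and an uncoded Can't say in its place, so 15 to 18 of 39 respondents could not record the top grade

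*Combined protocol and SAP*

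**What the plan says.** Appendix B prints an AIM and an IAM for each of three groups: patients, the health care team and peers.

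- **Staff AIM.** There are two levels of disagreement, then "Neither agree nor disagree Agree Can't say". All four items show codes 1 to 4 and nothing under the fifth heading, for example "I would like my patients enrolled in the HIT-Peer Delivery system. ① ② ③ ④".
- **Patient AIM.** The scale ends "Neither agree nor disagree Agree Completely agree", with codes 1 to 5, as in "I would like to be enrolled in the HIT-Peer Delivery system. ① ② ③ ④ ⑤".
- **Peer AIM.** The scale ends "Neither agree nor disagree Agree Complete agree", again with codes 1 to 5, as in "I like the HIT-Peer Delivery system. ① ② ③ ④ ⑤".
- **IAM.** All three versions have five levels with full agreement coded 5. This includes the IAM that follows the AIM on the staff form.

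Appendix A, Subaim 2.1, sets the sample at 39: five patients, five clinicians and one pharmacy respondent per site, plus six peers in total. Outcomes and Analysis in that section plans descriptive statistics, after which the design team reviews the results and refines the model. The documents give no code or handling rule for Can't say. They also give no reason for a different scale on the staff AIM.

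**The concern.** Acceptability is one of the two constructs that Sub-Aim 2.1 measures, and clinical staff are one of the three groups surveyed. On this form a clinician who fully agrees and one who merely agrees would tick the same box. That distinction cannot be recovered from completed forms. The same clinician then answers the IAM on a scale that does offer full agreement.

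Two reporting problems follow. A mean of the raw staff AIM codes would come from a 1 to 4 scale and could not be read beside a patient or peer mean from a 1 to 5 scale. And without a rule for Can't say, the analyst must decide afterwards whether those answers stay in the denominator of any percentage.

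**Working it through.** **1. Reproduce the sample size.** The inputs are the per-site numbers in Appendix A, Subaim 2.1, and three sites, one per county.

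- Patients: 5 × 3 = 15
- Clinicians: 5 × 3 = 15
- Pharmacy: 1 × 3 = 3
- Peers: 6
- Total: 15 + 15 + 3 + 6 = 39, which agrees with the stated target.

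**2. Count the respondents affected.**

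- Clinicians only: 15 / 39 = 38.5%
- Clinicians and pharmacy: (15 + 3) / 39 = 18 / 39 = 46.2%

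The range is needed because the documents do not say which form pharmacy staff complete. The higher count is plausible: Appendix B has no pharmacy form, and the role question on the staff form includes "Other staff (specify".

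**3. Set the six scales side by side.**

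| Scale | Disagree levels | Neutral | Agree levels | Codes |
|---|---|---|---|---|
| Patient AIM | 2 | 1 | 2 | 1–5 |
| Patient IAM | 2 | 1 | 2 | 1–5 |
| **Staff AIM** | **2** | **1** | **1, plus Can't say** | **1–4** |
| Staff IAM | 2 | 1 | 2 | 1–5 |
| Peer AIM | 2 | 1 | 2 | 1–5 |
| Peer IAM | 2 | 1 | 2 | 1–5 |

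The staff AIM is the only one of the six without a top grade.

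**4. Could text extraction explain it?** The fifth heading is legible and reads Can't say. The fifth cell is empty in all four rows, across a break in the table, while the other five tables kept their code 5. Had a 5 been lost, it would have stood under Can't say and not under full agreement. The missing top grade therefore does not depend on that cell.

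**5. What remains comparable?** On the staff AIM, agreement is code 4. On the patient and peer AIM it is code 4 or 5. The share answering Agree or higher therefore covers the same part of the scale on all three forms, provided the treatment of Can't say in the denominator is stated.

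**The case against.** The strongest reply is that little depends on this.

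- **No planned score is harmed.** A reader might infer that staff AIM totals or a pooled AIM mean would be capped below those of the other groups. The documents do not support that as a harm to the plan. The analysis lists descriptive topics and names no AIM total, no pooling and no between-group comparison. No AIM table has a total line; total lines appear only under the patient and peer IAM. This stands.
- **The questions differ anyway.** Staff are asked about their patients' needs and about enrolling their patients, while patients and peers answer for themselves. A fifth code aligns the range but not the content. This also stands, and limits what the correction achieves.
- **Item 2 is a separate matter.** It reads "The HIT-Peer Delivery system is appealing to both the patient and I healthcare provider", so it asks about two parties at once. A reader might want it split. That would give staff five items against four on the other forms and create a new mismatch, so it is not part of this point.
- **Can't say may be meant as unscored.** The blank cell fits that reading. It would settle the coding but not the denominator, and it would not restore the missing grade.
- **The form looks unfinished.** All three group forms still carry a placeholder for the revised prototype. Appendix A, Design Team Meeting #4, says the questionnaires are developed during the design process. This is a fair reason to treat the layout as a correctable slip, not as a deliberate choice.

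The synopsis describes the survey tools as adapted, but no section explains why the top grade would be dropped for staff alone.

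**Conclusion.** The point holds for the form as printed and for the AIM only. Used in this layout, it could not record full staff agreement on acceptability for 15 of 39 respondents, or 18 of 39 if pharmacy staff use it, and staff items would run from 1 to 4 against 1 to 5 for patients and peers. These counts assume that the enrolment target is met and describe who is affected, not the size of any effect.

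Two stronger readings are not supported. One is that staff acceptability results will be biased in a known direction: the documents give no basis for predicting how staff who fully agree, or who are unsure, would use the printed options. The other is that data have already been lost: the documents do not show whether this layout was used. No threshold, test or primary outcome depends on this form, so the correction is worth making but minor.

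**What to change.** **Before use:** print the staff AIM with the same five ordered options as the other forms, from 1 (completely disagree) to 5 (completely agree). If Can't say is kept, place it outside the scale as a separate unscored box and report how often it was ticked.

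**If staff forms are already collected:** report the staff AIM separately with its 1 to 4 range stated, or report the share answering Agree or higher, saying whether Can't say answers are in the denominator. Do not pool raw staff item scores with those of patients and peers.

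**Cost:** one form page to reprint and, if the form is already approved, to resubmit. Completed forms cannot be rescored to 1 to 5.

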### **Subaim 2.1: Evaluate the intervention for acceptability and appropriateness**

After the PT4A model prototype is created we will evaluate how applicable and workable the core components of PT4A will be more so in terms of cost, complexity, usability, and value.

Participants (targeted number of 39 in total will be enrolled), this will include representatives of the end users of our product, which includes: hypertension patients (5 per site), clinicians (5 per site), pharmacy (1 per site) and peers (6 in total). Participants will be recruited through convenience sampling within the 3 counties where we will conduct the study. Participants will be reimbursed for time and travel through PT4A funds during those sessions.

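### Two of the four staff acceptability items do not isolate the provider's own view, and no peer item directly asks about willingness to deliver the service

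*Combined protocol and SAP*

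**What the plan says.** Appendix A, Subaim 2.1, plans a survey in which a "targeted number of 39 in total will be enrolled". The groups are "hypertension patients (5 per site), clinicians (5 per site), pharmacy (1 per site) and peers (6 in total", recruited "within the 3 counties where we will conduct the study". Its Methods paragraph has the prototype presented from each stakeholder's standpoint, so that respondents understand their part in the model. Its Outcomes and Analysis paragraph plans descriptive statistics. The listed outcomes include interest in, or intention of, taking part, and the design team then uses the results to refine the model.

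Appendix B holds the three AIM forms.

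- **Patient form.** All four items are in the first person. Item 2 reads "The HIT-Peer Delivery system is appealing to me".
- **Staff form.** Item 1 is "The HIT-Peer Delivery system meets the patients needs". Item 2 asks whether the system "is appealing to both the patient and I healthcare provider". Item 3 asks whether the respondent likes the system, and item 4 whether the respondent would like their own patients enrolled.
- **Peer form.** The four items match the patient form. Item 1 is "The HIT-Peer Delivery system meets my needs" and item 4 is "I would like to be enrolled in the HIT-Peer Delivery system". Just before the items, the form reads out the peer's duties: delivering medication, giving support, recording progress and contacting clinicians.

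**The concern.** An attitude item is useful when it asks one person about one thing. Staff item 2 asks about two people. A provider who likes the system but doubts that patients will must average, choose one party or opt out, and the recorded value does not show which was done. Staff item 1 asks the provider to judge on someone else's behalf. That is a legitimate question, but it is not the provider's own acceptance.

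On the peer form the difficulty is role. A peer lives with hypertension, so can answer items 1 and 4, but the wording addresses the peer as a recipient. The outcome list for Subaim 2.1 includes intention to take part, and for a peer in this model taking part means delivering. The staff form did adapt item 4 to the provider's role; the peer form has no equivalent adaptation.

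At stake is how well the survey informs the design team at Meeting #5, before the pilot. The Appendix C peer interviews do ask about the experience of delivering, but only after the pilot.

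**Working it through.** **1. Reproduce the planned sample.** The inputs come from Appendix A, Subaim 2.1. The text does not say how many sites there are; I take one per county, giving 3.

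- Patients: 5 × 3 = 15
- Clinicians: 5 × 3 = 15
- Pharmacy: 1 × 3 = 3
- Peers: 6
- Total: 15 + 15 + 3 + 6 = 39, which matches the plan.

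With s sites the total is 11s + 6, so s = 3 is the only value that gives 39.

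**2. Count respondents per form.** I assume that pharmacy staff complete the health care team form, which has an option for other staff.

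- Staff form: 15 + 3 = 18, and 18/39 = 46.2%
- Peer form: 6, and 6/39 = 15.4%

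**3. Classify the items.**

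| Item | Patient form | Staff form | Peer form |
|---|---|---|---|
| 1 | own view | proxy for patients | own view, as recipient |
| 2 | own view | patient and provider combined | own view |
| 3 | own view | own view | own view |
| 4 | own view | own view, in provider role | own view, as recipient |

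**4. Count affected item-responses.** The total is 39 × 4 = 156.

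- Staff items 1 and 2: 18 × 2 = 36, and 36/156 = 23.1%
- Peer items 1 and 4: 6 × 2 = 12
- Both together: 36 + 12 = 48, and 48/156 = 30.8%

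The lower figure applies if first-person wording is enough for peers. The upper figure applies if the item must address the delivery role. The double-barrelled item alone accounts for 18 × 1 = 18, and 18/156 = 11.5%.

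**5. Look for a planned total or comparison.** The analysis paragraph gives no AIM scoring rule, cut-off or between-group test. The printed total-score lines sit under the appropriateness measure on the patient and peer forms, not under the AIM.

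**The case against.** The strongest defence is that little depends on these items. The analysis is descriptive, each item can be reported alone, and the survey feeds a design discussion in a formative study. Peers hear their duties immediately before answering, so items 2 and 3 can be answered from the delivery role. Peers also sit on the design team that discusses the peer role, and they are interviewed after the pilot. The staff form offers neutral and can't-say options, so item 2 can be answered, if ambiguously. The forms are visibly unfinished: each still has a placeholder for the updated prototype. Finally, rewording peer items 1 and 4 would make the peer form less like the patient form, with which it now agrees.

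Most of this stands, and it limits the point. It does not rescue staff item 2, where an ambiguous answer stays ambiguous however it is summarised. Nor does it supply a direct question on willingness to deliver before the pilot. The comparability argument is a good reason to add a peer question and leave the existing ones alone.

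A reader might infer three stronger claims, none of which the documents support.

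- **Acceptability is unreadable for all staff and peers**, 18 + 6 = 24 of 39 (62%). Staff items 3 and 4 and peer items 2 and 3 plainly ask the respondent's own view.
- **A planned comparison between groups is invalid.** No such comparison is planned.
- **Hiring of peers depends on this survey.** Nothing in the protocol says so, or says that the 6 peers surveyed are the ones hired for the pilot.

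**Conclusion.** The point holds as a matter of form wording, at low severity. On the staff form, one item is double-barrelled and one is a proxy, so half the items do not isolate the provider's own view for 18 of 39 respondents. On the peer form, two items ask about receiving the service and none directly asks about delivering it, for 6 of 39. The affected share is 23% to 31% of AIM item-responses, depending on how strictly the peer items are read.

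The count assumes one site per county and that pharmacy staff use the staff form. If they do not, the staff count is 15 and the range is 30 to 42 of 156 (19% to 27%). The forms ask different things of different groups, so a four-item total should not be pooled across them. The plan does not say that it would be, so this is a precaution.

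**What to change.** 1. **Staff item 2:** use the wording of the patient and peer forms, "The HIT-Peer Delivery system is appealing to me". This is the clearest gain.
2. **Staff item 1:** reword it to the provider's own view, or keep it and report it separately as the provider's opinion about patients.
3. **Peer form:** keep the four items and add one line asking whether the peer would like to deliver the service.
4. **Subaim 2.1, Outcomes and Analysis:** state that AIM results are reported by item and by group, with no total pooled across groups.

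The cost is a few lines on forms that are still drafts, one extra question for 6 peers, and slightly less uniform items across groups. If the survey has already been run, step 4 and a sentence stating the limitation are enough.
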